## **Study Protocol**

### *Trial design*

A care provider and participants blinded, parallel, randomized controlled trial with three groups was completed from September 2022 to April 2023. This trial is reported according to the CONSORT 2010 checklist for randomized controlled trials. All procedures were approved by the Ethics Committee of the Polytechnic Institute of Coimbra (CEIPC 6/2022).

### *Participants*

Swimmers were recruited from 2 national competitive teams in Portugal, affiliated with the Portuguese Swimming Federation during the 2022/2023 season. To be included in the sample, participants should be federated in the current season, aged between 16-35 years old, have a minimum of 5 years of experience in national competitions, and perform a minimum of 8 hours of weekly swimming training. Subjects who had performed at least 6 weeks of treatment such as physical therapy, injections, and medication, clinical situations such as a history of significant shoulder pain in the last 6 months, a history of traumatic shoulder injuries such as fractures, subluxations, cervical or thoracic conditions, previous shoulder surgeries, shoulder range of motion deficits, or neurological injuries, were excluded. All eligibility criteria were verified through an individual questionnaire before the sample selection. Each participant read and signed a written informed consent form based on the revised version of the 2013 Declaration of Helsinki. After being selected, all swimmers were weighed on a body composition scale Tanita RD-953, and measured using a stadiometer. The sample identity protection was preserved following the European Union General Data Protection Regulation – Regulation (EU) – 2016/679. This randomized controlled trial was conducted at the RoboCorp Laboratory at the Polytechnic Institute of Coimbra.

### *Intervention programs*

Twice a week, over 12-weeks, the two intervention groups carried out a strength training program with the 5 open kinetic chain exercises most often reported in the literature to prevent swimmer's shoulder: internal rotation (IR) at 90°, external rotation (ER) at 90°, scapular punches, T's, and Y's (Table

1). The weight program group performed these 5 exercises with two weights Domyos with 1, 2, 3, 4, or 5 kg (Fig. 1), and the elastic band program group with an elastic band Bodytone Power Band with 10, 15, 20, 25, or 30 kg (Fig. 2). The load used to perform the programs with elastic bands and weights was previously assessed and adjusted for each swimmer, corresponding to 75% of one repetition maximum (1 RM). After 6 weeks of program execution, each swimmer carried out another 1 RM test assessment, to verify the possibility of a load instrument progression.

[figure not shown]
Participants performed 2 sets of 10 valid repetitions in each exercise. The repetitions were considered valid when the swimmer reached the target range of motion (ROM) previously described for each exercise (Table 1). The concentric and eccentric phases of each exercise were performed for 5 seconds. A Tabata timer mobile application controlled this time. One minute of rest was preserved between different exercises and sets.

Programs were supervised by a sport physiotherapist independent of the study. Each athlete received individualized monitoring with a regular exercise technique correction in all sessions. The first session was in person and the following sessions have online monitoring through WhatsApp Messenger or Zoom Video Communications, Inc.

| Exercise  | Weight program                                                                                                                                                           | Elastic band program                                                                                                                                                                                                      |
|------------------|---------------------------------------------------------------------------------------------------------------------------------------------------------------------------------|----------------------------------------------------------------------------------------------------------------------------------------------------------------------------------------------------------------------------------|
| IR at 90°        | Started in a supine position, 90° of shoulders ABD, 90° of ER and 90° of elbows FLX. Movement: 90° of shoulders IR.                                                             | Started in a SP, 90° of shoulders ABD, 90° of elbows FLX and hands at the same height as shoulders. Elastic band should be fixed at shoulder height. Movement: 90° of shoulders IR (5 s) and return to the start position (5 s). |
| ER at 90°        | Started in a SP, 90° of shoulders ABD, 90° of elbows FLX and hands at the same height as shoulders. Movement: 90° of shoulders ER (5 s) and return to the start position (5 s). | Started in a SP, 90° of shoulders ABD, 90° of elbows FLX and hands at the same height as shoulders. Elastic band should be fixed at shoulder height. Movement: 90° of shoulders ER (5 s) and return to the start position (5 s). |
| Scapular punches | Started in a SP, 90° of shoulders ABD, 90° of elbows FLX and hands at the same height as shoulders. Movement: Elbow EXT (5 s) and return to the start position (5 s).           | Started in a SP, 90° of shoulders ABD, 90° of elbows FLX and hands at the same height as shoulders. Elastic band should be fixed at shoulder height. Movement: Elbow EXT (5 s) and return to the start position (5 s).           |
| T's              | Started in a SP, 90° of shoulders FLX and maximum elbows EXT. Movement: 90° of shoulders HABD (5 s) and return to the start position (5 s).                                     | Started in a SP, 90° of shoulders FLX and maximum elbows EXT. Elastic band should be fixed at shoulder height. Movement: 90° of shoulders HABD (5 s) and return to the start position (5 s).                                     |
| Y's              | Started in a SP, 90° of shoulders FLX and maximum elbows EXT. Movement: 90° of shoulders HABD and maximum shoulders FLX (5 s) and return to the start position (5 s).           | Started in a SP, 90° of shoulders FLX and maximum elbows EXT. Elastic band should be fixed at shoulder height. Movement: 90° of shoulders HABD and maximum shoulders FLX (5 s) and return to the start position (5 s).           |

**Table 2.**  
Description of 5 exercises that constitute the weight and elastic band programs

SP – standing position; s – seconds; ABD – abduction; ER – external rotation; IR – internal rotation; FLX – flexion; EXT –extension; HABD – horizontal abduction.

**Fig. 1.** Illustration of the 5 exercises included in the weight program: A) IR at 90°, B) ER at 90°, C) Scapular punches, D) T's, E) Y's.

**Fig. 2.** Illustration of the 5 exercises included in the elastic band program: A) IR at 90°, B) ER at 90°, C) Scapular punches, D) T's, E) Y's.

### *Control group*

[figure not shown]
The control group performed a sham intervention, twice a week, for 12-weeks. This intervention consisted of 2 sets of 10 repetitions of 5 shoulder mobility exercises, without preventive aim, normally carried out in warm-up before training: shoulder maximum flexion and extension, horizontal abduction and adduction starting from 90° of shoulder abduction, maximum IR and ER starting from 90° of shoulder abduction, circumduction of the shoulder in a clockwise direction and circumduction of the shoulder in a counterclockwise direction. There was no progression after 6-weeks of this sham intervention. The coach of the respective team checked the execution of the exercises, but there was no individualized monitoring with a regular exercise technique correction by a physiotherapist.

### *Outcomes and testing procedures*

Before (T0) and after 12-weeks (T1) of interventions and control procedures, concentric and eccentric peak torque (PT) of IR and ER of the dominant and non-dominant shoulder was performed through an isokinetic dynamometer Biodex System 3 (Biodex Medical Systems, New York), at 60°/s, 120°/s and 180°/s.

Previously to strength evaluations, each swimmer did a 10-minute warm-up of a general upper limb joint mobilization. The isokinetic dynamometer assessment was carried out with the swimmer in the supine position. Half of the swimmers started the assessment with the dominant shoulder, and the other half started with the non-dominant shoulder. Previously, this order was randomized for each swimmer. The upper extremity was positioned with the shoulder abducted to 90° and the elbow flexed to 90° so that the dynamometer's axis was aligned with the longitudinal axis of the humerus. The athlete's trunk and evaluated arm were stabilized using velcro straps to avoid compensatory movements (Fig. 3). Gravity correction was not used for this testing position because the ER and IR shoulder muscles moved with and against gravity as they applied force. Strength was tested through 145° of range of motion (ROM), between 80° of ER and 65° of IR, to obtain the PT variation in the maximum rotational ROM available. The tests started every time with the shoulder in 80° of ER. The concentric strength was tested first, followed by the eccentric strength test. The order of the angular velocity test was increased (60°/s-120°/s-180°/s) to preserve an ascending difficulty during the evaluations. A hard cushion deceleration control was selected to allow the subject the greatest availability of velocity attainment before deceleration. The procedure was explained to all athletes before the start of testing, with emphasis on exerting maximal effort within an individual's tolerance. After this, swimmers performed 3 submaximal trials to familiarize themselves with the ROM and the accommodating resistance of the dynamometer. Both concentric and eccentric tests at different velocities consisted of 5 maximal-effort reciprocal repetitions. Standardized verbal instructions and encouragement were given to all subjects. A minute rest period between different tests was preserved.

The PT was used to characterize the strength values of shoulder rotator muscles, defined as the maximum torque produced by the shoulder at any point of the ROM. To analyze shoulder rotator strength balance, the ER:IR ratio was calculated – the quotient between PT values of the ER:IR multiplied by 100. For this investigation, the conventional concentric ER : concentric IR ratio and functional eccentric ER : concentric IR were calculated.

**Fig. 3.** Subject position and stabilizing during the isokinetic dynamometer strength assessment.

### *Sample size*

The G\*power software (Franz Faul, Edgar Erdfelder, Axel Buchner, Universitat Kiel, Kiel, Germany, version 3.1.9.4) was used to calculate the sample size, considering an alpha level of 0.01, a power of 0.99, and an effect size (Cohen's *d*) of 2.81 based in a similar previous study. Thus, a minimum of 24 swimmers – 8 for different groups – was necessary.

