## **Statistical Analysis Plan**

The data was previously filtered (smoothing option) and windowed at 95% of test velocity. Data analysis was performed using the Acqknowledge 4.1 software. The mean and standard deviation (SD) of the PT assessments in the 5 repetitions of different muscles (IR and ER), actions (concentric and eccentric), and angular velocities (60°/s, 120°/s, and 180°/s) for both sides were calculated. Subsequently, the conventional concentric ER : concentric IR ratio and the functional eccentric ER : concentric IR ratio were verified for these three angular velocities.

All statistical analysis was carried out using IBM SPSS Statistics 27 software. Mean and SD were used for sample characterization. The Shapiro-Wilk test was used to verify the normality of the sample distribution. The homogeneity of variance between the three groups was verified for the sample characterization variables and the main outcome at T0, through the One-Way ANOVA or the Kruskal-Wallis tests. After this, an inter-group analysis in T0 and T1 and an intra-group analysis between T0 and T1 was made for dominant and non-dominant shoulders. For an inter-group analysis, the One-Way ANOVA or the Kruskal-Wallis tests were applied to compare differences between the three groups in T0 and T1. For an intra-group analysis, the Paired Sample T-test or the Wilcoxon test was applied to compare differences in each group between T0 and T1. A p-value  $\leq 0.05$  was considered as the level of significance for each difference in PT and ER:IR ratios.

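### Does leaving the contrast behind d = 2.81 unstated, and sizing at alpha 0.01 while testing at 0.05, undermine the 24-swimmer sample size?

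*Combined protocol and SAP*

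**What the plan says.** The Sample size section of the protocol gives the inputs in one sentence: G*Power, "considering an alpha level of 0.01, a power of 0.99, and an effect size" expressed as Cohen's d "of 2.81 based in a similar previous study". From these it derives at least 24 swimmers, 8 per group. It does not name the test, its sidedness, the outcome (peak torque or an ER:IR ratio), or whether d is a difference between groups or a change over time.

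The Statistical Analysis Plan has two families of comparison: "an inter-group analysis in T0 and T1 and an intra-group analysis between T0 and T1 was made". Between groups, "the One-Way ANOVA or the Kruskal-Wallis tests were applied to compare differences between the three groups in T0 and T1". Within groups, "the Paired Sample T-test or the Wilcoxon test was applied to compare differences in each group between T0 and T1". A p-value of at most 0.05 "was considered as the level of significance for each difference in PT and ER:IR ratios". The SAP does not mention 0.01.

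Under Trial design, the three-group trial is described as already completed, between September 2022 and April 2023.

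**The concern.** Two things catch the eye.

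**The effect size has no stated contrast.** A d of 2.81 means different things in the two families. As a gap between groups in units of the between-swimmer SD, it bears directly on the T1 three-group test, which is the comparison that randomisation supports. As a T0-T1 change divided by the SD of that change, it bears only on the paired tests, and the T1 three-group test then has no stated power. The distinction affects how a non-significant T1 result is read: at power above 0.99 it speaks against a large effect, and at much lower power it says little.

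**The two significance levels differ.** The sample size uses 0.01 and the analysis uses 0.05, with no explanation. On a quick reading this looks like a calculation made for a different analysis.

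**Working it through.** **Inputs from the documents.** d = 2.81, alpha = 0.01 and power = 0.99, giving 8 per group and 24 in total (Sample size); analysis threshold 0.05, with ANOVA or Kruskal-Wallis between groups and paired t or Wilcoxon within groups (SAP). The T0-T1 correlation r is not given and is varied below as an assumption.

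**Step 1. Reproduce the 8.** For a two-sample t-test the noncentrality is d × √(n/2) on 2n − 2 degrees of freedom. At two-sided 0.01:

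- n = 7: 2.81 × √3.5 = 5.257, 12 df, critical t 3.055, power 0.9722.
- n = 8: 2.81 × √4 = 5.62, 14 df, critical t 2.977, power 0.9903.

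The smallest n reaching 0.99 is 8, and 3 × 8 = 24 is the stated total. A one-sided test also gives 8 (0.9892 at 7, 0.9967 at 8).

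**Step 2. Can a within-group test give 8?** For a paired t-test the noncentrality is d × √n on n − 1 degrees of freedom. At two-sided 0.01:

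- n = 6: power 0.9676.
- n = 7: 2.81 × √7 = 7.435, power 0.9950.

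The paired t-test therefore needs 7 two-sided, and 6 one-sided. A Wilcoxon signed-rank test at its usual relative efficiency for normal data (3/π) also needs 7 (0.9906). It needs 8 only two-sided and at its minimum efficiency of 0.864 (0.9701 at 7, 0.9940 at 8). The Sample size section mentions neither a Wilcoxon test nor an efficiency setting.

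**Step 3. Power of the planned three-group test if 2.81 is a between-group gap.** With 8 per group, ANOVA has 2 and 21 df and noncentrality 24f².

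- Two groups equal, the third 2.81 SD away: f = 2.81 × √2/3 = 1.325, 24f² = 42.11.
- Third mean midway: f = 2.81/√6 = 1.147, 24f² = 31.58.

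At 0.05, power is 0.9999 and 0.998 respectively. Simulated Kruskal-Wallis power (40,000 runs, normal data) is 0.9996 and 0.996. At 0.01, ANOVA power is 0.998 and 0.982.

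**Step 4. The same test if 2.81 is a change divided by the SD of the change.** Assume the control group does not change and the SD is the same at T0 and T1. The SD of the change is then SD × √(2(1 − r)), and the T1 gap in SD units is 2.81 × √(2(1 − r)). Power at 0.05 with 8 per group:

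| Assumed r | T1 gap (SD) | ANOVA, programmes equal | ANOVA, third mean midway | Kruskal-Wallis, equal / midway |
|---|---|---|---|---|
| 0.5 | 2.81 | 0.9999 | 0.998 | 0.9996 / 0.996 |
| 0.7 | 2.18 | 0.991 | 0.960 | 0.985 / 0.942 |
| 0.8 | 1.78 | 0.937 | 0.850 | 0.915 / 0.810 |
| 0.9 | 1.26 | 0.674 | 0.542 | 0.630 / 0.499 |

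At r = 0.95 ANOVA power falls further, to 0.38 and 0.30. ANOVA power stays at 0.99 or above until r exceeds 0.705 (programmes equal) or 0.606 (midway).

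**Step 5. The two alpha levels.** At 0.05 two-sided, the two-sample calculation needs 6 per group (0.9918; 5 per group gives 0.972). Sizing at 0.01 gave 8. With 8 per group, two-sample power at 0.05 is 0.9994.

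**The case for a change.** The strongest case for acting is that a match on n does not prove where d came from. A T0-T1 effect size from the earlier study could have been typed into a two-group calculation, and 8 would still come out. The SAP does not list a two-sample t-test, so even the natural reading leaves the step to the three-group test unstated. If the less favourable reading is true, power for the randomised comparison could be well below 0.99, and comparing T0-T1 change between groups would restore it to 0.996 or more.

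The first part stands: the documents do not settle where 2.81 came from, and nothing elsewhere in them supplies the missing description. The rest carries less weight. Step 3 shows that the move from two groups to three costs almost nothing at 0.05. The low power figures need two unsupported assumptions together: the within-group reading, and a correlation near 0.9 or above. The change-score comparison has more power than the T1 test only when r exceeds 0.5, would be added after the trial ended, and concerns the choice of analysis more than the sample size. A non-significant T1 result in a finished trial is better judged by its confidence interval than by the power that was planned.

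**Conclusion.** No change to the plan follows. The Sample size section is under-described, but its figure is not shown to be wrong. The simplest calculation from the stated inputs, a two-group comparison at two-sided 0.01, returns exactly 8 per group with power 0.9903. If 2.81 is a between-group gap, the planned three-group tests at 0.05 have power of 0.996 to 0.9999 across ANOVA and Kruskal-Wallis. The within-group route to 8 needs a worst-case Wilcoxon efficiency, since the paired t-test needs only 7.

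The difference between 0.01 and 0.05 is not a contradiction. A design may be sized at a stricter level than it is tested at, and here that adds 2 swimmers per group (8 against 6).

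The remaining uncertainty is the source of d. If it is a change divided by the SD of the change, power of the T1 test runs from 0.9999 down to about 0.50 as the assumed correlation rises from 0.5 to 0.9, given an unchanged control group and equal SDs. The trial is complete, so enrolment cannot move, and writing down the G*Power settings would alter no test, threshold or number. This is a gap in description that an analyst can fill from the calculation's own output.

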### *Randomisation and blinding*

An initial screen survey was carried out on the two swimming teams before the sample selection. After the application of eligibility criteria, the eligible swimmers were divided into a weight program group, an elastic band program group, or a control group. The allocation to each group was performed through stratified randomization according to the team, sex, and main swimming style. This design was used to equate the possible effects of these three variables in results and was prepared with a computer random number generator by a member of the research team. Then, all swimmers carried out the T0 assessment moment through the isokinetic dynamometer. To minimize fatigue bias during the assessments, half of the swimmers started the evaluation with the dominant shoulder, and the other half started with the non-dominant shoulder. Previously, this order was randomized for each swimmer. After T0 moment, for 12-weeks the two experimental interventions were applied and supervised by a blinded sports physiotherapist external to the study, without knowledge of the previous procedures and the study objectives. It only explains in detail the interventions and the load that should be used by each athlete considering the 1RM test previously performed by a member of the research team. The participants were unaware of the existence of other sample groups. At the end of the 12-weeks, all swimmers who

completed the proposed interventions carried out the T1 strength assessment through the isokinetic dynamometer. All T0 assessment procedures were maintained in T1 moment.

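### The T1 group comparison omits team, sex and style, the factors used to stratify allocation: absolute peak torque is tested conservatively if sex is balanced and without correction if it is not

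*Combined protocol and SAP*

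**What the plan says.** Under *Randomisation and blinding*, the protocol says: "The allocation to each group was performed through stratified randomization according to the team, sex, and main swimming style". It gives the reason: "This design was used to equate the possible effects of these three variables in results". Block size and the number of style categories are not stated. *Participants* gives the number of teams: "Swimmers were recruited from 2 national competitive teams in Portugal".

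The Statistical Analysis Plan describes the between-group comparison as follows: "the One-Way ANOVA or the Kruskal-Wallis tests were applied to compare differences between the three groups in T0 and T1". Neither test takes a covariate, and the plan names no ANCOVA, stratified test or T0 adjustment. Groups are also compared at T0 on sample characteristics and the main outcome, but no correction follows from that check. Within each group, "the Paired Sample T-test or the Wilcoxon test was applied to compare differences in each group between T0 and T1".

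Peak torque is analysed as recorded; *Outcomes and testing procedures* describes no scaling to body mass. The ER:IR ratio is "the quotient between PT values of the ER:IR multiplied by 100".

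**The concern.** The plan treats three factors as important enough to constrain the allocation and then leaves them out of the comparison that the allocation was meant to protect. For absolute torque, sex is the factor most likely to matter. Two different things can then happen.

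- **Sex balanced over arms.** The arm means are fair, but the sex difference is counted as random error. A programme effect well below the planned one is more easily missed.
- **Sex unbalanced over arms.** Part of the T1 difference between arms is a sex difference, and no term removes it.

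The ratios should suffer less, because a proportional sex difference in both torques cancels: (k·ER)/(k·IR) = ER/IR. In the paired tests each swimmer is their own control, so they are not touched.

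**Working it through.** **The plan's own figure.** *Sample size* gives alpha 0.01, power 0.99, d = 2.81 and 8 per group. A two-sided two-sample t-test (noncentral t) gives power 0.990 at n = 8 and 0.972 at n = 7, so 3 × 8 = 24 reproduces. I use 8 per arm below, with the SAP's alpha of 0.05.

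**Assumptions.** The documents do not give the sex gap D (in within-sex SD), the sex mix, the style categories, the block method, effects below 2.81 or the T0–T1 correlation. All are assumed and shown as ranges. Errors are normal with within-sex SD 1.

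**Why the direction depends on balance.** Let p be the share of one sex in an arm. Sex adds D²·8·Σp(1−p) to the within-arm sum of squares (21 df) and D²·8·Σ(p−p̄)² to the between-arm sum of squares (2 df).

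- 4/4/4: within 8·3·0.25·D² = 6D², between 0. Expected mean squares are 1 between and 1 + 6D²/21 within. At D = 1 the ratio is 1/1.286 = 0.78: conservative.
- 6/4/2: within 8(0.1875 + 0.25 + 0.1875)D² = 5D², between 8(0.0625 + 0 + 0.0625)D² = 1.0D². At D = 1 the ratio is (1 + 0.5)/(1 + 5/21) = 1.5/1.238 = 1.21: inflated.
- 5/4/3: within 5.75D², between 0.25D². At D = 1 the ratio is 1.125/1.274 = 0.88: still conservative, although the extreme arms are shifted by 0.25D.

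**Simulation of the planned tests** (mostly 40,000 trials per setting; ranges show repeated runs).

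| Sex gap D | 0.5 | 1 | 1.5 | 2 |
|---|---|---|---|---|
| Type I, ANOVA, 4/4/4 | 4.1–4.2% | 2.4–2.5% | 0.9% | 0.2–0.3% |
| Type I, Kruskal-Wallis, 4/4/4 | 3.7% | 2.1% | 0.8% | 0.1–0.2% |
| Type I, ANOVA, 6/4/2 | 5.6–5.8% | 7.2–7.7% | 8.7–9.3% | 9.6–10.0% |
| Shift of extreme arms from sex alone, 6/4/2 (SD) | 0.25 | 0.50 | 0.75 | 1.0 |
| Power, both programmes +2.0 SD, 4/4/4 | 0.97 | 0.95 | 0.90 | 0.79 |
| Power, +1.5 SD, 4/4/4 | 0.80–0.81 | 0.73 | 0.59–0.60 | 0.42–0.43 |
| Power, +1.0 SD, 4/4/4 | 0.43–0.44 | 0.34 | 0.22 | 0.12 |

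With sex and team in the model under exact balance, type I error is about 5% throughout and power is about 0.98, 0.82 and 0.46 for the three effects. Adjusted type I error is also about 5% at 6/4/2.

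At d = 2.81, read as within-sex SD, planned-test power is at least 0.95 for every gap. The lowest value is 0.954, for arm means 0, 1.405, 2.81 at a 2 SD gap. If 2.81 is already in mixed-sex SD units, there is no shortfall at that effect.

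**How likely imbalance is.** Two teams × two sexes × an assumed four styles gives 16 strata for 24 swimmers, so many blocks would be incomplete. With permuted blocks of 3 in each stratum:

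| | Four equal styles | 60/15/15/10 mix | Two styles |
|---|---|---|---|
| Count of one sex differs by ≥3 between arms (sex and team random) | 37% | 30% | 14% |
| Same, 12 of each sex fixed | 34% | 26–27% | 10% |
| Differs by ≥4, 12 of each sex fixed | 16% | 10% | 3% |

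Averaged over such allocations, type I error is 4.5%, 3.5%, 2.4%, 1.7% with 16 strata and 4.5%, 3.1%, 1.8%, 0.9% with 8, for D = 0.5 to 2.

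**Adding the T0 value** (effect 1.0 SD, gap 1 SD).

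| T0–T1 correlation | 0.3 | 0.5 | 0.7 | 0.8 |
|---|---|---|---|---|
| Planned test | 0.34 | 0.34 | 0.34 | 0.35 |
| Group + T0 | 0.44 | 0.54 | 0.74 | 0.88 |
| Group + T0 + sex + team | 0.48 | 0.56 | 0.74 | 0.88 |

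**The case against.** The strongest reply is that the missing stratification factors are the lesser part of the problem. Once T0 is in the model, sex and team add visible power only at T0–T1 correlations of about 0.5 or below. This stands, and is why T0 belongs in the fix. The T0 models were, however, compared at a 1 SD gap only.

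Second, the 6/4/2 example is an unfavourable one. The 14% to 37% frequencies are for a difference of 3 or more. At exactly 3 (6/3/3 or 5/5/2) type I error is only about 5.3% to 6.3%, and at 5/4/3 it is below 5%. Those frequencies must therefore not be read as the chance of a 7% to 10% error. Averaged over allocations the planned test is conservative, so there is no overall false-positive problem. This also stands. The inflation is conditional on the imbalance obtained, which is what the analyst of one completed trial has to deal with.

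Third, the loss does not bite at d = 2.81, and every input about sex is assumed. That is correct. But 2.81 is a very large effect, taken from one source ("2.81 based in a similar previous study"), and smaller effects would be of interest. Only a sex effect has been quantified here; nothing is shown for team or style.

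Fourth, the T0 comparison might reveal a large torque imbalance. It might, but with 8 per arm it has little power to do so, and the plan attaches no action to it.

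**Conclusion.** The point holds. The T1 between-group tests ignore the factors on which allocation was stratified. For absolute peak torque they are conservative when sex is balanced and uncorrected when it is not.

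The size depends on an assumed sex gap. At no gap nothing is lost. At 1 SD with exact balance, the nominal 5% test runs at about 2.5% and power for a 1 SD effect is 0.34 instead of about 0.46. At 1 SD with a 6/4/2 split, the extreme arms differ by 0.5 SD with no treatment effect. Even a mild imbalance shifts the estimate, although the test may stay below 5%.

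The planned effect remains detectable, and the paired tests stand as they are. The weakness should be corrected because it limits what can be read from either a null or a positive torque result. It does not invalidate the trial.

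**What to change.** Replace the T1 between-group test with a linear model: T1 = group + T0 value of the same measure + sex + team. With 24 swimmers at T1 this leaves 24 − 1 − 2 − 1 − 1 − 1 = 18 residual df; restate the figure for the number actually retested, since only completers were measured at T1. Put style, collapsed if needed, in a sensitivity analysis, because a term for every team × sex × style stratum is not feasible at this size. Say in the SAP what is done if the residuals are clearly non-normal, since Kruskal-Wallis is the plan's present answer to that. Tabulate sex, team and style by arm. Leave the paired tests as they are.

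The documents state that the trial "was completed from September 2022 to April 2023", so no change to the randomisation is proposed. If results have been seen, report this model beside the planned tests and label it as added after completion.

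The cost is SAP wording and a rerun in the same software, with no new data. The sex and team terms use two residual df: with no sex gap and a 1.0 SD effect, power is 0.467 instead of 0.472.

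### Three crossed stratification factors for about 24 swimmers in three arms do not assure the claimed balance or 8 per group, and the T1 tests leave those factors out

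*Combined protocol and SAP*

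**What the plan says.** Randomisation and blinding states that "the eligible swimmers were divided into a weight program group, an elastic band program group, or a control group" by "stratified randomization according to the team, sex, and main swimming style". The stated purpose is balance: "This design was used to equate the possible effects of these three variables in results". A member of the research team prepared the list with a random number generator, after eligibility had been screened in both teams. The section gives no style categories, allocation ratio, block size or rule for strata with fewer than three swimmers, and no step that fixes the arm totals.

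Participants gives two teams. Sample size gives the target: "a minimum of 24 swimmers – 8 for different groups – was necessary". The number actually randomised is not stated.

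The Statistical Analysis Plan compares the three groups at T0 and again at T1 by One-Way ANOVA or Kruskal-Wallis. Team, sex and style enter none of these tests.

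**The concern.** A stratum with one or two swimmers cannot be spread evenly over three arms. When many strata are that small and each is randomised separately, their remainders add up, giving unequal arms and leftover imbalance on the factors that the stratification was meant to control. The balance claim and the 8 per arm then depend on an allocation method that the plan does not describe.

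The analysis offers no safeguard. Sex is a plausible strong predictor of shoulder peak torque. A T1 test without sex leaves any imbalance in the group comparison. It also keeps the between-sex variance in the error term, although the design has already removed part of that variance from the differences between arms. The likely result is a test that is too conservative and less precise than the same data allow.

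**Working it through.** **1. The plan's sample size.** Inputs from Sample size: "considering an alpha level of 0.01, a power of 0.99" and a Cohen's d "of 2.81 based in a similar previous study". For a two-sided two-sample t-test, the noncentrality is d × √(ab/(a+b)) with a + b − 2 degrees of freedom.
- 8 v 8: 2.81 × √4 = 5.62, df 14, power 0.990.
- 7 v 7: 2.81 × √3.5 = 5.26, df 12, power 0.972.

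So 8 per arm is the smallest size reaching 0.99, and 3 × 8 = 24. The stated figure reproduces.

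**2. Number of strata.** 2 teams × 2 sexes × k styles = 4k. The plan does not give k, so 2 to 5 is assumed. The mean stratum size is 24/(4k).

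**3. Simulated allocation of 24 swimmers.** Assumptions: teams and sexes 50:50, styles equal or skewed (the last column uses equal styles), independent permuted blocks of 3 within each stratum.

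| Styles | Strata | Mean per stratum | Occupied strata with <3 | Exact 8/8/8 | Smallest arm ≤6 | Mean gap in proportion of one sex |
|---|---|---|---|---|---|---|
| 2 | 8 | 3.0 | 38–39% | 15% | 24–25% | 0.15 |
| 3 | 12 | 2.0 | 61–62% | 10–11% | 37–38% | 0.19 |
| 4 | 16 | 1.5 | 70–76% | 8–9% | 44–48% | 0.21 |
| 5 | 20 | 1.2 | 75–83% | 6–7% | 48–54% | 0.23 |

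In an arm of 8, gaps of 0.15 and 0.23 correspond to 8 × 0.15 = 1.2 and 8 × 0.23 = 1.8 swimmers.

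**4. Comparators under the same assumptions.**
- Unstratified 8/8/8: mean sex gap about 0.30, or 8 × 0.30 = 2.4 swimmers.
- One list sorted by stratum (team first, then sex) with blocks of 3 running on across strata: 8/8/8 in every run. The mean range is about 1.3 swimmers of one sex (1.3/8 = 0.16) and about 0.67 swimmers for team, the first sorting key (0.67/8 = 0.08).

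**5. Power with uneven arms, two-sided alpha 0.01, d = 2.81.** 7 v 9 gives 0.989. For 6 v 9, 2.81 × √(54/15) = 5.33, df 13, power 0.979. 6 v 8 gives 0.969.

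**6. Effect of leaving sex out of the T1 test.** Outcomes were simulated with no group effect under the step 3 allocation with equal styles. Sex explains 30% or 50% of the variance (assumed), and the test is at 0.05.

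| Styles | ANOVA, 30% | ANOVA, 50% | With sex and team in the model |
|---|---|---|---|
| 2 | 2.1% | 0.8% | 4.9–5.1% |
| 3 | 2.5% | 1.4% | 4.8–5.1% |
| 4 | 3.0% | 1.8% | 5.0% |
| 5 | 3.0% | 2.3% | 5.0% |

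The unadjusted ANOVA rejects too rarely; the adjusted model is close to 5% throughout.

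**The case against.** The strongest reply is that the plan does not say each stratum had its own list. Both teams were screened before allocation, so the full list could have been known, and a list sorted by stratum with continuous blocks is also stratified. It gives 8/8/8 every time. The number of styles is unstated, 24 is a minimum, and with 36 swimmers and three styles only about 38–41% of occupied strata hold fewer than three. This stands: the plan cannot be said to fail at balance, only to leave it unassured. A larger sample does not by itself equalise the arms, however. With independent blocks, equal arms still occur in only about 6–15% of runs at 36.

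A reader might infer that such fine stratification balances sex worse than no stratification. Counting swimmers can suggest this, because counts mix arm size with sex mix. On the proportion of one sex per arm, which is what shifts an arm mean, stratification is better at every number of styles tried (0.15–0.23 against about 0.30).

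A reader might also infer a serious loss of power, such as a fall to 0.926. That figure needs two arms of 6, which with 24 swimmers puts 24 − 12 = 12 in the third. Likelier splits such as 6 v 9 keep 0.979 at alpha 0.01. At the 0.05 level used in the Statistical Analysis Plan, even 6 v 6 gives 0.992.

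Finally, the groups are compared at T0 on sample characteristics and the main outcome. That may reveal imbalance, but it does not adjust the T1 comparison.

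**Conclusion.** The point holds as a gap in the allocation method and an omission in the analysis. With three or more styles, most occupied strata would be too small for one swimmer per arm; with two styles, they would not. If strata were randomised independently in blocks of 3, 8/8/8 would be uncommon (about 7–15%) and a sex gap of 0.15–0.23 would remain on average. The claim of equated factors and the 8 per arm are therefore not assured by what is written. The documents do not support saying that balance was unattainable, that stratifying did harm, or that the planned power is materially lost.

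The firmer part is the T1 analysis. Omitting sex and team leaves imbalance uncorrected and the error term too large. The type I error is about 1–2.5% over most of the assumed range and 3% at its edge, against a nominal 5%. This is conservatism and lost precision; it does not inflate false positives. The size depends on sex explaining 30–50% of peak-torque variance, which the documents do not give. The effect on the ER:IR ratios could differ. The simulation covers the ANOVA, not the Kruskal-Wallis alternative.

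**What to change.** **Analysis (free improvement).** Replace the T1 between-group test with a linear model (ANCOVA) containing group, sex and team. Judge normality on its residuals. No new data are needed. The cost is two degrees of freedom: with 24 swimmers, the residual goes from 24 − 3 = 21 to 24 − 5 = 19. Style is left out because its unstated number of levels could use up several more.

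**Reporting.** Trial design describes the trial as completed, so allocation is already done. State the style categories, allocation ratio, block or other method, the handling of strata below three and the number randomised. Tabulate team, sex and style by arm. If the T1 results have already been seen, say that the adjusted model was added afterwards. This takes one paragraph and one table.

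**Allocation, for a repeat or extension.** Because eligibility is known beforehand, replace independent per-stratum lists with one draw from the 8/8/8 allocations that meet preset limits on team, sex and style counts. Alternatively, use a stratum-sorted list with blocks running across strata. Sorting by sex first should give sex the tighter balance seen for the first key in the working. This needs a short program and no extra visits or staff, but the rule must be written down in advance and the balancing factors carried into the analysis.
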